### 5.2.2 Exclusion criteria

Patients will be considered ineligible for this study if they meet any of the following criteria:

Patients with a known hypersensitivity to SST analogs or any component of the pasireotide LAR or SQ formulations.

Patients with known malabsorption syndrome, short bowel or chologenic diarrhea not controlled by specific therapeutic means.

Patients with abnormal coagulation (PT or a PTT elevated by 30% above normal limits).

Patients on continuous anticoagulation therapy. Patients who were on anticoagulant therapy must complete a washout period of at least 10 days and have confirmed normal coagulation parameters before study inclusion.

Patients with symptomatic cholelithiasis.

Patients who are not biochemically euthyroid.

Patients with known history of hypothyroidism are eligible if they are on adequate and stable replacement thyroid hormone therapy for at least 3 months.

Serum magnesium  $\geq$  ULN

QT-related exclusion criteria:

QTcF at screening  $>$  470 msec

Patients with a history of syncope or family history of idiopathic sudden death

Patients who have sustained or clinically significant cardiac arrhythmias

Risk factors for Torsades de Pointes such as hypokalemia, hypomagnesemia, cardiac failure, clinically significant/symptomatic bradycardia, or high-grade AV block

Patients with concomitant disease(s) that could prolong QT such as autonomic neuropathy (caused by diabetes, or Parkinson's disease), HIV, cirrhosis, uncontrolled hypothyroidism or cardiac failure

Family history of long QT syndrome

Concomitant medications known to prolong the QT interval.

Potassium  $<$  or  $=$  to 3.5

Patients who have any severe and/or uncontrolled medical conditions or other conditions that could affect their participation in the study such as:

Patients who have Uncontrolled diabetes as defined by HbA1c $>$ 8%\* despite adequate therapy

Patients with the presence of active or suspected acute or chronic uncontrolled infection or with a history of immunodeficiency, including a positive HIV test result (ELISA and Western blot). An HIV test will not be required; however, previous medical history will be reviewed.

Non-malignant medical illnesses that are uncontrolled or whose control may be jeopardized by the treatment with this study treatment.

Liver disease such as cirrhosis, decompensated liver disease, chronic active hepatitis or chronic persistent hepatitis.

Baseline ALT or AST  $>$ 3x ULN

Patients with life-threatening autoimmune and ischemic disorders.

Uncontrolled hypertension

Patients who have a history of a primary malignancy, with the exception of locally excised non-melanoma skin cancer and carcinoma in situ of uterine cervix. (Patients who have had no evi-

dence of disease from primary cancer for 3 or more years are allowed to participate in the study.)

History of pancreatitis

Patients with a known history of hepatitis B or C

Presence of Hepatitis B surface antigen (HbsAg)

Presence of Hepatitis C antibody (anti-HCV)

Patients with a history of, or current, alcohol misuse/abuse within the past 12 months

Known gallbladder or bile duct disease, acute or chronic pancreatitis

Patients who have any current or prior medical condition that may interfere with the conduct of the study or the evaluation of its results in the opinion of the Investigator or the Sponsor's Medical Monitor

Use of an investigational drug within 1 month prior to dosing

Patients with a history of non-compliance to medical regimens or who are considered potentially unreliable or will not be able to complete the entire study

Females who are pregnant or lactating, or are of childbearing potential (defined as all women physiologically capable of becoming pregnant) and not practicing an effective method of contraception/birth control. Sexually active males must use a condom during intercourse while taking the drug and for 2 months after the last dose of the study drug and should not father a child in this period. A condom is required to be used also by vasectomized men in order to prevent delivery of the drug via seminal fluid. Effective contraception methods include:

Use of oral, injected or implanted hormonal methods of contraception

Placement of an intrauterine device (IUD) or intrauterine system (IUS)

Barrier methods of contraception: condom or occlusive cap (diaphragm or cervical/vault caps) with spermicidal foam/gel/film/cream/ vaginal suppository

Total abstinence or

Patient sterilization (male or female)

## **6 Treatment**

### **6.1 Investigational and control drugs**

#### **6.1.1 SOM230C / Placebo**

Pasireotide LAR (long-acting release) IM depot injection:

Inactive ingredients of pasireotide LAR include: mannitol, carmellose sodium (carboxymethyl-cellulose sodium), poloxamer 188 and water for injection. Inactive ingredients of pasireotide SQ include: mannitol, tartaric acid, sodium hydroxide and water for injection. For detailed information on pasireotide, please refer to Sections 1.3 and 1.4 of the Pasireotide Investigator Brochure.

Placebo:

The placebo will have an appearance similar to SOM230.

**6.1.2 How supplied**

Pasireotide LAR IM depot injections will be supplied in open-label packaging by Novartis as a powder in vials containing 20 mg, 40 mg and 60 mg labeled as SOM230 LAR or placebo, with ampoules containing 2mL of vehicle (for reconstitution).

No syringes or needles will be provided with the pasireotide study drug supplies.

The placebo will be supplied (as powder) for mixing with injection solution by Novartis.

**6.1.3 Preparation and storage**

Prior to reconstitution, vials should be brought to room temperature. Pasireotide LAR should then be prepared as shown in Table 4.

**Table 4 Handling and preparation of pasireotide LAR dose**

Dose	Volume to be injected
20 mg	1 x 20 mg vial + 2 mL vehicle; whole volume to be injected
40 mg	1 x 40 mg vial + 2 mL vehicle; whole volume to be injected
60 mg	1 x 60 mg vial + 2 mL vehicle; whole volume to be injected

Doses should be prepared and administered immediately after preparation. *For additional details regarding preparation, refer to Appendix 4.*

Novartis will supply pasireotide LAR as long as the patient remains on study, shows continuous benefit from treatment, and there are no safety concerns. Medication labels will comply with the legal requirements of the U.S. and will be printed in English. The storage conditions for pasireotide LAR will be described on the medication label. Bottles must be stored in a safe, secure location.

All study medication will be supplied to Mayo by Novartis. Mayo Research Pharmacy will be responsible for storage of medication. An accurate record of the date and amount of study drug dispensed to each subject must be available for inspection at any time.

All drug supplies are to be used only for this protocol and not for any other purpose. Unless specifically instructed by Novartis, the investigator must not destroy any drug labels. All unused or damaged drug will be sent to ALMAC Clinical Services. The storage condition for the study drug will be described on the medication label.

#### 6.1.4 Administration

Pasireotide LAR/placebo will be administered IM intragluteally, every 4 weeks. The starting dose will be 60 mg. The reconstitution has to be performed just prior to administration of the suspension. A minimal standing time can be tolerated for the reconstituted suspension in the vial. Prior to administration, the reconstituted suspension in the vial should be shaken again before withdrawal in the syringe. The IM injection must be given immediately after withdrawal of the reconstituted suspension from the vial to the syringe.

All dosages prescribed and dispensed to the patient and dose changes during the study must be recorded. The investigational study drugs used in the course of this trial are pasireotide LAR (SOM230C)/ placebo. Novartis will supply pasireotide LAR and placebo free of charge for study participants.

#### 6.2 Treatment arms

There will be stratified randomization for PLD patients with ADPLD and ADPKD (see Table 5):

All participants who receive the placebo during year one will be given the option to continue on study to receive active study drug for years two and three. Thus, all participants will be receiving SOM230 years two and three.

**Table 5 Stratified randomization**

Disease Group	SOM230	Placebo
ADPLD	8	4
ADPKD	24	12
Total	32	16

The initial assessment will be derived on a clinical basis as some individuals with ADPLD also may have kidney cysts.

### 6.3 Patient numbering

Randomization numbers will be provided by the study statistician to Research Pharmacy.

The recommended blinding methods are as following: randomization data are kept strictly confidential until the time of treatment un-blinding. This information will not be accessible with the following exceptions: pharmacist, as needed for reconstitution; an independent biostatistician, who will perform the analysis or database lock; the investigator and only immediately relevant study staff after LPLV. The identity of the treatments will be concealed by the use of study treatments that are all identical in packaging, labeling, schedule of administration and appearance after reconstitution. Once the last patient completes LPLV, the database will be cleaned and an interim or final database lock will be placed. Subsequently, the database will be unblinded to the investigator and the sponsor.

### 6.4 Treatment blinding

Pasireotide LAR/ placebo will be administered IM every  $28 \pm 2$  days in the clinic only by an unblinded study nurse. The current recommended starting doses for pasireotide LAR is 60 mg for NET and 40 mg or 20 mg for acromegaly.

Medication labels for SOM230 LAR and placebo will comply with the US legal requirements. There will be no information about the patient provided on the study drug label.

Study drug, SOM230 /placebo IM depot injections will be supplied by Novartis as a powder in vials containing 20 mg, 40 mg and 60 mg labeled as SOM230 LAR or placebo, with ampoules containing 2mL of vehicle (for reconstitution).

For this blinded study, patients, investigator, site personnel and data analysts will be blinded to the identity of the treatment from the time of randomization until protocol specified schedule of un-blinding. An unblinded pharmacist or a study nurse identified prior to start of the study are to be the only site personnel to reconstitute the study drug.

Un-blinding will only occur in the case of patient emergencies, after LPLV for the investigator only, and after final database lock (at end of year 1, and at end of year 3). Pasireotide LAR is to be stored in a secure locked area while under the responsibility of the investigator. An authorized person at the investigational site must record receipt and dispensation of the study medications. The vials for pasireotide LAR IM depot formulation must be stored at refrigerated temperatures between 2°C and 8°C (36°F-46°F) and protected from light until the time of use. The pasireotide LAR drug product kit should remain at room temperature for 30-60 minutes prior to preparation of the drug suspension. For pasireotide LAR, the reconstitution must be performed just prior to administration of the suspension. Doses should be administered immediately after preparation. For doses higher than 40 mg, contents of 2 or 3 low dosage vials will be combined into one or two injections. Each injection will have maximum volume of 2 ml. A maximum of three vials will be combined per injection and a maximum of 2 injections, at 2 separate injection sites of each patient, will be given to reach the dosing level.

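### Sections 6.3 and 6.4 contradict each other on whether the investigator may see treatment codes before the database is cleaned and locked, and on whether the analyst is blinded

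*Combined protocol and SAP*

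**What the plan says.** Section 6.4 blinds everyone who handles or analyses data until the scheduled un-blinding: "patients, investigator, site personnel and data analysts will be blinded to the identity of the treatment". It then names the occasions on which the blind may be broken: "Un-blinding will only occur in the case of patient emergencies, after LPLV for the investigator only, and after final database lock". The locks are dated "at end of year 1, and at end of year 3".

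Section 6.3 keeps the randomization data confidential, with exceptions. Besides the pharmacist, these are "an independent biostatistician, who will perform the analysis or database lock; the investigator and only immediately relevant study staff after LPLV". A few lines later it gives a sequence: "Once the last patient completes LPLV, the database will be cleaned and an interim or final database lock will be placed". It continues: "Subsequently, the database will be unblinded to the investigator and the sponsor".

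LPLV does not appear in the list of abbreviations and is not defined elsewhere. Section 4 makes year 1 double-blind and years 2 and 3 open-label.

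**The concern.** Between the last patient's visit and database lock, queries are answered, doubtful values are resolved, and adverse-event grade and relationship are finalised. If the people doing this hold the codes, their judgements can lean with the arm without anyone intending it.

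The adverse-event data matter most here. Section 3.1 places adverse events under the primary objectives. Sections 8 and 10.2 tabulate them by severity and by the investigator's view of relationship, and compare the arms with Fisher's exact test. The trial has one centre (Section 5.1) and a sponsor-investigator (Section 6.10), so no other site would dilute the effect of an unblinded judgement.

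The analyst's position raises a second question. Section 10.2 takes the t-test as the default and considers a transformation or the Wilcoxon test if normality or equal variance looks untenable. It gives no criterion and no point in time for that decision. A person who knows the arms could make the choice after seeing which result each option gives.

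**Working it through.** No figure in the plan bears on this point, so there is nothing to reproduce numerically. The check sets the statements side by side.

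**Step 1: order of events for the investigator.**
- Section 6.4 and the exception list in Section 6.3 ("the investigator and only immediately relevant study staff after LPLV"): LPLV, then codes may be released. Neither makes lock a condition.
- Closing sentences of Section 6.3: LPLV, then cleaning, then lock, then codes.

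Two statements permit access between LPLV and lock, and one places it after lock. Staff cannot follow both. Reading a silent lock requirement into the LPLV clause of Section 6.4 does not help: un-blinding after lock is already a separate item in the same list, so the clause would then add nothing.

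**Step 2: what LPLV could mean.**

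| Reading | Consequence for year-1 data |
|---|---|
| (a) LPLV is the last month-12 visit, and the exception applies | Codes may be known during year-1 cleaning |
| (b) LPLV is the last visit of the 36-month study | The year-1 lock comes first; the clause touches only the later, open-label data |
| (c) The closing sentences of Section 6.3 govern | Un-blinding follows lock; no exposure by this route |

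Reading (a) is favoured over (b) for two reasons. Section 6.3 has LPLV followed by either an interim or a final lock, and Section 6.4 dates locks at years 1 and 3. An interim lock that follows LPLV implies an LPLV for year 1. The text favours this reading but does not establish it.

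**Step 3: the analyst.** Section 6.3 excepts "an independent biostatistician, who will perform the analysis or database lock" and sets no time limit, although the investigator's exception in the same sentence has one. Section 6.4 counts data analysts among the blinded. The documents do not say whether this biostatistician is one of those analysts, or is the study statistician who supplies the randomization numbers. Someone who performs the analysis is naturally read as an analyst, and on that reading the two sections conflict.

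**Step 4: what is exposed under reading (a).**
- Liver volume: largely protected. Sections 7.4.1.1 and 7.4.1.2 have volumes measured by readers blind to arm.
- Missing month-12 scans: Section 10.2 has a rule. They are left out of the volume comparison and counted as non-response for the responder endpoint.
- Adverse-event grade and relationship: exposed for items still open at the last month-12 visit.
- Other query resolution: exposed to the same extent.
- Choice of test: exposed if the analyst holds codes when it is made.

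**Step 5: a separate route to the year-1 arm.** Sections 4 and 7 repeat the early safety assessments in year 2 for former placebo patients only. Section 4.1 expects recruitment over about 6 months. A patient enrolled at the start reaches month 12 at calendar month 12, and one enrolled at month 6 reaches it at calendar month 18. The gap is 18 − 12 = 6 months. The arm of early enrollees may therefore become apparent from their visit schedule up to about 6 months before the last month-12 visit.

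**The case against.** The strongest reply is that the only full sequence in the plan, at the end of Section 6.3, is the correct one, so this is loose drafting and not a decision to un-blind early. A reader might infer from the LPLV clause that the plan has year-1 data finalised by people who know the arms. The documents do not support that: early release is one side of a contradiction, and year-1 exposure also needs reading (a).

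A reader might also infer that the analyst is definitely both blinded and a code holder, or that Section 10.2 hands the test choice to that person. The first is a natural reading but is not stated. On the second, Section 10.2 assigns the choice to no role, sets a default, and names the conditions for leaving it.

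Nor do the documents support a claim that the primary endpoint is broadly at risk, given the blinded readings and the rule for missing scans. The adverse-event exposure should not be inflated either. Sections 7.5.1 and 8.1.1.1 have events evaluated and reassessed at each visit, so most judgements should be made before LPLV.

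These limits stand, but they do not remove the point. Two statements still permit access before lock, and nothing in the plan says which rule prevails.

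**Conclusion.** The blinding rules are wrong as written. They allow the investigator, and under Section 6.3 certain study staff, to hold codes before cleaning and lock, and they also say the opposite. The analyst's status is unresolved in the same way.

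The documents allow no numerical estimate of bias. The trial plans 48 patients, but the number of queries and adverse-event decisions open at the last month-12 visit is not given and may be small. The main exposure is investigator-assessed adverse-event data and the choice of test for quantitative endpoints; exposure of the liver-volume result is limited.

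The year-1 consequence assumes that LPLV means the last month-12 visit. The analyst conflict assumes that the biostatistician in Section 6.3 is one of the data analysts in Section 6.4. If either assumption is wrong, the matching part reduces to a missing definition that should still be supplied.

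**What to change.** 1. Delete the LPLV exception in Sections 6.3 and 6.4. Apart from emergencies and the designated unblinded pharmacist, nurse and list-holding statistician, no one who enters, cleans, grades or analyses data should receive codes before the year-1 database is locked.
2. Define LPLV separately for year 1 and year 3, and list it among the abbreviations.
3. State by role which statistician holds the randomization list and which performs the analysis. The analyst receives codes only after lock.
4. Fix the choice among t-test, transformation and Wilcoxon test at a blinded review before the year-1 lock.

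The cost is wording, one blinded review, and the investigator's wait from the last month-12 visit until lock, which the closing sentences of Section 6.3 already provide for. If the list holder and the analyst are at present the same person, a second statistician is needed; the documents do not settle this.

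These changes do not close the route in Step 5. Protecting the year-1 blind against the repeat safety schedule needs its own provision, and the protocol should say how it will be handled.

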**Table 6 Handling and preparation of pasireotide LAR different doses**

Dose (mg)	Volume to be injected
20	1 x 20 mg vial +2mL vehicle: whole volume to be injected
40	1 x 40 mg vial + 2mL vehicle: whole volume to be injected
60	1 x 60 mg vial + 2mL vehicle: whole volume to be injected

A matching placebo for the pasireotide LAR formulation will be provided by Novartis. Syringes will be concealed by pharmacy to maintain blinding.

## 6.5 Pasireotide LAR dose adjustment

We will use the oncology dosing (including NETs) as already described above, pasireotide LAR at 60 mg every 28 days being the recommended starting dose for oncological indications. If tolerability issues occur, the treatment dose may be reduced to pasireotide LAR at 40 mg with next scheduled injection. Patients requiring a dose reduction can return to the higher dose once the tolerability issue is resolved. However, patients not able to tolerate the minimum pasireotide LAR dose of 20 mg are recommended to be discontinued from study.

All dose changes must be recorded on the Dosage Administration Record CRF. Table 7 outlines the dose reduction steps for pasireotide.

Emergency un-blinding will be done at the discretion of the Principal Investigator [REDACTED] in cases where she feels it is necessary for the safety of the patient.

### 6.5.1 Permitted study drug adjustments

Toxicity will be assessed using the NCI-CTC for Adverse Events, version 3.0 (CTCAEv3.0, <http://ctep.cancer.gov/forms/CTCAEv3.pdf>). For patients who are unable to tolerate the protocol-specified SOM230C dosing schedule, dose-adjustment guidelines are given below.

## 6.6 Pasireotide LAR / placebo dose adjustment

As already described above, pasireotide LAR/placebo at 60 mg every 28 days is the recommended starting dose for oncological indications (including NETs). If tolerability issues occur, the treatment dose may be reduced to pasireotide LAR at 40 mg with next scheduled injection. Patients requiring a dose reduction can return to the higher dose once the tolerability issue is resolved. However, patients not able to tolerate the minimum pasireotide LAR dose of 20 mg are recommended to be discontinued from study.

All dose changes must be recorded on the Dosage Administration Record CRF. Table 7 outlines the dose reduction steps for pasireotide.

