**Table 7 Guideline for treatment of patients experiencing adverse events**

Recommended dose modifications for pasireotide/ placebo	
Worst toxicity CTCAE Grade* (value)	Recommended dose modification any time during a cycle of therapy
No toxicity	Maintain dose level
Hematologic	
Neutropenia (ANC)	
Grade 1 (ANC < LLN - 1500/mm  )	Maintain dose level
Grade 2 (ANC < 1500 - 1000/mm  )	Maintain dose level
Grade 3 (ANC < 1000 - 500/mm  )	Omit dose until resolved to ≤ Grade 2, then ↓ 1 dose level 
 
• If resolved ≤ 7 days, then maintain dose level
 
• If resolved > 7 days, then ↓ 1 dose level
 

Grade 4 (ANC < 500/mm  )	Omit dose until resolved to ≤ Grade 2, then ↓ 1 dose level 
 
• If resolved ≤ 7 days, then maintain dose level
 
• If resolved > 7 days, then ↓ 1 dose level
 

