**Thrombocytopenia**

Grade 1 (PLT < LLN - 75,000/mm  )	Maintain dose level
Grade 2 (PLT < 75,000 - 50,000/mm  )	Maintain dose level
Grade 3 (PLT < 50,000 - 25,000/mm  )	Omit dose until resolved to ≤ Grade 1, then ↓ 1 dose level 
 
• If resolved ≤ 7 days, then maintain dose level
 
• If resolved > 7 days, then ↓ 1 dose level
 

Grade 4 (PLT < 25,000/mm  )	Omit dose until resolved to ≤ Grade 1, then ↓ 1 dose level
Febrile neutropenia (ANC < 1.0 x 10  /L, fever ≥ 38.5°C)	Omit dose until resolved, then ↓ 1 dose level

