**Hepatic See also section 7.5.4.1****Bilirubin**

Grade 1 (< 2 x baseline value)	Maintain dose level
Grade 2 (2-3 x baseline value)	Omit dose until resolved to ≤ Grade 1, then 
 
• If resolved ≤ 7 days, then maintain dose level
 
• If resolved > 7 days, then ↓ 1 dose level
 

Grade 3 (> 3.0 - 10.0 x ULN)	Omit dose until resolved to ≤ Grade 1, then 
 
• If resolved ≤ 7 days, then maintain dose level
 
• If resolved > 7 days, then ↓ 1 dose level
 

Grade 4 (> 10.0 x ULN)	Omit dose and discontinue patient from study treatment

NOTE: If grade 3 or 4 hyperbilirubinemia is due to the indirect (unconjugated) component only, and hemolysis as the etiology has been ruled out as per institutional guidelines (e.g. review of peripheral blood smear and haptoglobin determination), then ↓ 1 dose level and continue treatment at the discretion of the investigator

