**Pancreatic****Pancreatitis**

Grade 1	Maintain dose level
---------	---------------------

Grade 2	Maintain dose level
Grade 3	Omit dose and discontinue patient from study treatment
Grade 4	Omit dose and discontinue patient from study treatment
Amylase and/or lipase	
Grade 1 (> ULN - 1.5 x ULN)	Maintain dose level
Grade 2 (> 1.5 - 2.0 x ULN)	Maintain dose level
Grade 3 (> 2.0 - 5.0 x ULN)	For asymptomatic: Omit dose until resolved to ≤ Grade 1, then 
 
• If resolved ≤ 7 days, then maintain dose level
 
• If resolved > 7 days, then ↓ 1 dose level
 
 For symptomatic: Omit dose and discontinue patient from study treatment
Grade 4 (> 5.0 x ULN)	Omit dose and discontinue patient from study treatment A CT scan or other imaging study to assess the pancreas, liver and gallbladder must be performed within 1 week of the first occurrence of any ≥ CTCAE grade 3 of amylase and/or lipase.
Endocrine/metabolic	
Fasting plasma glucose (FPG) or 2-hour postprandial capillary glucose (PPG)	
FPG <126 mg/dL or PPG < 140 mg/dL	Maintain dose level
Grade 1 (> ULN – 160 mg/dL)	appendix 2 section 12.2.
Grade 2 (> 160 – 250 mg/dL)	appendix 2 section 12.2.
Grade 3 (> 250 – 500 mg/dL)	appendix 2 section 12.2.
Grade 4 (> 500 mg/dL)	appendix 2 section 12.2.
Cardiac	
Cardiac - prolonged QTc interval	

 
• QTcF > 480 ms and ≤ 500 ms
 
• QTcF > 500 msec
 
	
If at any time a QTcF > 480 ms and ≤ 500 ms is observed a cardiology consultation must be sought to re-evaluate the abnormal ECG finding.
 
 
1. Triplicate ECGs (2-3 minutes apart) need to be taken approximately 1 hour after the initial ECG.
 
2. If the mean QTcF is > 500 ms, the patient must postpone study treatment until a cardiologist has re-evaluated the ECG.
 
3. The re-evaluation of ECG needs to be done as soon as practical but within 7 days of the initial abnormal ECG.
 
4. If the cardiologist confirms a mean QTcF > 500 ms, the patient must be discontinued.
 

Cardiac general	
Grade 1 or 2	Maintain dose level
Grade 3	Omit dose until resolved to ≤ Grade 1, then ↓ 1 dose level
Grade 4	Omit dose and discontinue patient from study treatment
Other adverse events	
Grade 1 or 2	Maintain dose level
Grade 3	Omit dose until resolved to ≤ Grade 1, then ↓ 1 dose level

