 Height required only at pre-study 12 lead ECG & interpretation at screening and ½ hour after first injection. Repeat ECG on 21st day after injection for the first 3 months then every third month. All ECGs are faxed to the Mayo Clinic ECG Core lab. Includes WBC with differential Comprehensive fasting metabolic panel includes: albumin, total bilirubin, calcium, CO2, (bicarbonate) chloride, creatinine, BUN, potassium, total protein, sodium, AST, ALT, ALP,, and glucose. Liver function tests are assessed at baseline (if baseline LFTs are **done within 7 days of day 1 of treatment** they do not have to be repeated on day 1), day 22 after first injection, day 29, day 50, 57 and 85. After day 85 and the 4th LAR Injection, monitoring should follow the existing protocol schedule. Day 22 & 50 LFTs must be available & assessed prior to dosing on days 29 (2nd injection) and 57 (3rd injection). Only in patients with associated PKD. Hemoglobin A1C is done at baseline and 3 monthly Thyroid function is also acceptable if checked within 30 days of the screening visit Bi-weekly cyclosporin levels will be monitored for the first month in enrolled patients who are on this medication (mail in test) Plasma glucose is required 6 hours after first injection. Monitor FPG or finger stick at baseline and at 21st day of treatment for first 3 months. Monitor FPG or finger stick monthly (or as clinically appropriate), thereafter.

-  Women of childbearing potential only (urine pregnancy test). If CT scan is needed, a negative pregnancy result will need to be obtained prior to performing the CT. For women of child bearing potential who will be having an MRI – a pregnancy test is not required at month 12.
-  SOM230/placebo IM injections will be given every 28 days, +/- 2 days.
-  No gallstone assessment is needed on visits where MRI is performed, as gallstones will be detected on MRI if present.
-  In year 2, safety assessments for patients crossing over from placebo to SOM 230 will be required. These will be per the same schedule after the first SOM230 injection as was performed in year 1 for all patients enrolled.

At a minimum the following safety evaluations (Table 9) are to be included in all protocols.

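### Sections 6.5 and 6.6 allow the dose back up once a toxicity has resolved, but eleven Table 7 rows can start the reduction only after resolution, and nothing says which rule governs

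*Combined protocol and SAP*

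**What the plan says.** Sections 6.5 and 6.6 carry the same paragraph on dose adjustment. A reduction may start at the next injection: "If tolerability issues occur, the treatment dose may be reduced to pasireotide LAR at 40 mg with next scheduled injection". A return is then allowed: "Patients requiring a dose reduction can return to the higher dose once the tolerability issue is resolved". Resolution is the only condition given. Both sections close by pointing to the table: "Table 7 outlines the dose reduction steps for pasireotide".

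Table 7 sets out what to do by toxicity and grade. For cardiac general grade 3, other adverse events grade 3 and thrombocytopenia grade 4 the instruction is "Omit dose until resolved to ≤ Grade 1, then ↓ 1 dose level". For febrile neutropenia it is "Omit dose until resolved, then ↓ 1 dose level". The grade 3 and 4 neutropenia rows open with "Omit dose until resolved to ≤ Grade 2, then ↓ 1 dose level" and then split according to whether recovery took more than 7 days. The table contains no step back up.

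Section 2.1 mentions reduction but not return. Section 2.2 says only that placebo is monitored and adjusted monthly in like manner.

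**The concern.** The text and the table give resolution opposite roles. In 6.5 and 6.6 it permits the higher dose. In the Table 7 rows it is the point at which the lower dose starts. Because 6.5 and 6.6 cite Table 7 for the reduction steps, the two read as parts of one rule set, so a reader cannot simply treat them as separate regimes.

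What is at stake is the dose given after a serious toxicity. Two members of staff could follow the protocol faithfully after the same grade 3 event and give different doses, with neither in deviation. The row for other adverse events matters most here, because it takes in any event without a row of its own. Diarrhea is one such event. Section 6.10 describes gastrointestinal problems as the most commonly reported events, though mostly grade 1 or 2. Appendix 1 says that treatment continues only when diarrhea has resolved, but not at which dose level.

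**Working it through.** The plan gives no figure to reproduce, so the main check is to set the passages side by side.

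**Step 1. Which Table 7 rows step down after resolution?**

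| Row | Recovery required before resuming | Step down |
|---|---|---|
| Thrombocytopenia grade 4 | grade 1 or lower | always |
| Febrile neutropenia | resolved, no grade given | always |
| Cardiac general grade 3 | grade 1 or lower | always |
| Other adverse events grade 3 | grade 1 or lower | always |
| Neutropenia grade 3 | grade 2 or lower | if over 7 days |
| Neutropenia grade 4 | grade 2 or lower | if over 7 days |
| Thrombocytopenia grade 3 | grade 1 or lower | if over 7 days |
| Creatinine 2–3 × ULN | grade 1 or lower | if over 7 days |
| Bilirubin grade 2 | grade 1 or lower | if over 7 days |
| Bilirubin grade 3 | grade 1 or lower | if over 7 days |
| Amylase/lipase grade 3, asymptomatic | grade 1 or lower | if over 7 days |

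That is 4 + 7 = 11 rows. The count follows the 7-day sub-bullets. In the two neutropenia rows and the thrombocytopenia grade 3 row, the opening line steps down without condition and so clashes with its own sub-bullet, which is a separate inconsistency.

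One entry works differently. The note on indirect hyperbilirubinemia does not wait for recovery: "then ↓ 1 dose level and continue treatment at the discretion of the investigator". The glucose rows defer to Appendix 2, whose algorithm figures are not shown, so they could not be checked.

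**Step 2. Is the return condition met when the reduction starts?**
- Febrile neutropenia: yes. Table 7 and 6.5/6.6 both speak of resolution with no grade attached.
- Any other row where the event has cleared completely: yes.
- Recovery only to the grade 1 or 2 threshold: arguable. Sections 6.5 and 6.6 do not define what counts as resolved.
- Recovery in 7 days or less in the seven split rows: no clash, because the sub-bullets keep the dose.

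**Step 3. Does anything reconcile them?** The documents give no minimum time at the reduced dose, no separate criterion for going back up, no definition of resolution for this purpose and no order of precedence.

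**Step 4. Illustration of cumulative dose.** Assumptions, none of them a forecast: 13 year-1 injections (365 / 28 = 13.04, from "SOM230/placebo IM injections will be given every 28 days, +/- 2 days"), a start at 60 mg, and one step to 40 mg at the fourth injection.

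| Reading | No injection missed | Fourth injection omitted, step-down at the fifth |
|---|---|---|
| Reversed at once | 13 × 60 = 780 mg | 12 × 60 = 720 mg |
| Reversed after one lower dose | 12 × 60 + 40 = 760 mg | 11 × 60 + 40 = 700 mg |
| Held | 3 × 60 + 10 × 40 = 580 mg | 3 × 60 + 9 × 40 = 540 mg |

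Held against reversed at once: (780 − 580) / 780 = 25.6%, or (720 − 540) / 720 = 25.0%. The size depends on the chosen injection. With none missed and the step at injection k, the gap is 20 × (14 − k) / 780, which runs from 30.8% at k = 2 to 2.6% at k = 13.

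**The case against.** The strongest reply is that the rules apply in sequence. Table 7 says what to give on resuming, and the word *return* implies that the lower dose has already been given. A patient at the first injection after the event then has nothing to return from. Sections 6.5 and 6.6 may also have a different case in mind: a discretionary reduction with no dose omitted, where resolution comes after the reduction and the return sentence works as it stands.

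This has force. A reader might infer that the protocol plainly permits both doses at the same injection in every row. The documents do not support that, because the sequential reading is natural and most rows ask only for partial recovery. The sequential reading does not remove the conflict, however. It delays the return by one injection, since the condition was met before the reduction began and no other condition is stated. In the illustration it still separates 760 from 580 mg. Nothing in the text confines the return sentence to discretionary reductions.

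Section 6.8 also narrows the scope. It requires discontinuation for grade 3 or higher hematology or chemistry abnormalities that the investigator judges clinically significant, which takes some patients out of the laboratory rows. It does not automatically remove cardiac or other grade 3 events.

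Finally, Table 7 is headed as recommended and 6.6 uses permissive wording. That makes strict contradiction too strong a term, but it leaves the dose after the event undetermined.

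**Conclusion.** The point holds as an unreconciled dosing rule. In four Table 7 rows, and in seven more when recovery took over 7 days, a resolved event still leads to a lower dose, while 6.5 and 6.6 make resolution sufficient for going back up. The match is exact for febrile neutropenia and for fully cleared events. For partial recovery it depends on an undefined word.

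Three stronger readings should be resisted:
- A reader might infer that Table 7 lowers doses only after resolution. The indirect hyperbilirubinemia note shows otherwise.
- A reader might take the roughly 25% gap as an effect on the trial. It is one hypothetical patient with an arbitrary injection number, and the documents give no frequency for these events.
- A reader might infer that the treatment comparison is biased. The documents do not show this. The primary analysis follows intent-to-treat principles (section 10.2), the same text governs both blinded arms in year 1, and dose changes are recorded on a CRF. What is left unclear is the dosing rule that the active arm represents.

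The importance is moderate: the text bears on the dose after serious toxicity, and the remedy is cheap.

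**What to change.** Reconcile 6.5, 6.6 and Table 7 so that all three state the same rule on whether the return sentence applies to Table 7 reductions and, if so, how. Say what counts as resolved for that purpose, given that Table 7 works with grade thresholds and 6.5 and 6.6 do not. Nothing here presumes that a condition beyond resolution is needed, or that reductions should be held; that choice is left to the sponsor-investigator.

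The cost is amendment wording in two paragraphs and a note to Table 7. No change to sample size, visits or analysis is involved.
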